14.3.1 Outcome measures

The primary outcome in a trial of weight loss maintenance strategies will be change in body weight (kg) between 6 month and 18 or 24 month follow ups, i.e. after a period of weight loss.

Proposed secondary outcome measures for a trial are:

- Changes in minutes of moderate activity per week and total energy expenditure (assessed by accelerometer)
- Body Mass Index (BMI)
- Waist circumference
- Self-reported quality of life (EQ-5D-5L ³⁹)

In addition, data will be collected on any newly diagnosed medical conditions or changes in medication during the study period, as well as any other weight management services or interventions used (cointerventions), and smoking cessation attempts (which can cause substantial weight gain).

14.3.2 Economic evaluation

Proposed economic evaluation measures for a trial are

- Cost-effectiveness of the SkiM intervention (using an NHS / Payer perspective)
- Resource use for intervention delivery (the costs and time requirements of training facilitators and delivering the intervention)
- Costs for health and social care utilisation (primary and secondary care contacts, social care contacts and medication usage) over study period, using a bespoke Service Use Inventory.

Page 23 of 61

All participant outcomes will be assessed at baseline (0 months) and at 6 and 12 months. Outcome questionnaires will be self-completed but checked for completeness by a researcher during assessment visits, and body measurements will be taken by the researcher. See Appendix 2 for the full schedule of quantitative measurements.

15 PROCESS EVALUATION

15.1 Design

Aims: In line with the recommendations of the MRC Framework and guidelines for development and evaluation of complex interventions^{31, 40} we will conduct a process evaluation with the following aims:

- a) To elicit experiences of engaging with the intervention approaches, including identification of processes of lifestyle behaviour change and maintenance that work well or badly
- b) To identify other potential processes that may influence the success of the maintenance component of the interventions
- c) To identify possible barriers to engagement with the intervention programmes and ways in which the interventions could be improved
- d) To examine the fidelity of intervention delivery and receipt

15.2 Participant interviews and session recordings

We will explore the research aims above using individual semi-structured interviews at baseline and at 6 and 18 months after baseline. A short interview will be conducted with all participants at baseline. A more in-depth interview will be used at follow-up, with 12-15 participants from each intervention arm (6-8 interviews per arm per cohort), interviewing the same participants at both time points where possible and using a mixture of face-to-face and telephone interviews depending on location /availability of participants. A topic guide will be developed in consultation with our service user advisory group. In the follow-up interviews, we will purposively sample to achieve diversity in age, gender and success or failure in maintaining weight loss. 'In-vivo' recordings will also be made of all intervention contacts (with permission from participants and intervention providers), using digital recording equipment operated by the facilitator. Recordings of group sessions will be audio-visual, but any 1:1 contact recordings will be audio-recorded only. This will allow assessment of intervention fidelity and provide a basis for providing formative feedback to our facilitators, as well as providing anonymised examples of good practice for future provider training. The session recordings will also be a source of 'triangulation' data to add depth to the narratives derived from the individual interviews (the use of session recording data has been found in prior studies to add substantial depth to participant interview data⁴¹). Consent to take part in the study (for both participants and facilitators) will include consent for these recordings to be made.

15.3 Process measures

Self-report questionnaires will be used to measure several intervention processes (i.e. to see whether the theoretical change processes which the intervention is designed to deliver are working as planned). These will be developed by the research team, but may include the following:

- Self-report Habit Index (automaticity subscale)
- Engagement in self-regulation activities (including frequency of self-weighing, use of goal-setting and problem-solving strategies taught in the intervention)
- Self-efficacy for lapse management (prevention and recovery)
- Self-efficacy for managing external influences on weight-related behaviours
- Perceived tension /difficulty maintaining weight (scale to be constructed by the research team based on their synthesis of qualitative research in weight loss maintenance)
- Resilience in weight management (scale to be constructed by the research team based on their synthesis of qualitative research in weight loss maintenance)
- Weight-related identity beliefs (scale to be constructed by the research team based on their synthesis of qualitative research in weight loss maintenance)

15.4 Intervention fidelity assessment

The primary data to assess intervention fidelity will be the session recordings (see section 15.224). Following procedures used in previous trials of complex interventions by the research team^{42, 43}, an intervention fidelity measure will be developed and applied. The procedure involves a) identifying the behavioural techniques and delivery processes that are associated with the intervention (as defined by the intervention development work conducted prior to this study) and b) using the Dreyfus skill acquisition scale⁴⁴ to rate the competence of providers in delivering the targeted techniques and delivery processes. This produces a score of 0 to 6 for each targeted element of the intervention process. The scale is anchored such that a score of 3 is considered acceptable, 0 is non-existent and 6 is perfect performance (which is unusual). Two experts in behaviour change intervention will listen to the set of recordings for each participant (or group). They will apply the fidelity measure to rate competence in each element of intervention in each contact and across the whole set of recordings. They will mark sections of the recording that may be useful for informing feedback to the facilitators (examples of good or poor practice, or which illustrate the intended intervention processes) by noting the timestamp of the digital recording and keywords to reflect the content. This will allow the construction of formative feedback and prompts for discussion for each facilitator. These sections may also be transcribed (and anonymised) so that they can be used to inform future training. Where processes are consistently difficult to deliver and performance does not improve with feedback, or if the facilitators strongly feel that part of the intervention is not working/not workable, this may suggest changes to the intervention or to the delivery procedures. We will not be able to reprint the intervention materials until the end of this study, but we can adapt the delivery procedures and elements of programme content, giving the facilitators a chance to develop their skills over the course of the study.

Recordings of group sessions will be augmented by two field visits per programme presentation, in which a Researcher observes the session. This will enable aspects of group interactions and dynamics to be observed that would be difficult to capture through an audio-visual recording. The researcher

will make notes during and after each visit, based upon a checklist of criteria relating to fidelity and to other issues that may impact upon intervention effectiveness.

15.5 Intervention receipt

We will assess receipt /enactment of the targeted intervention processes by:

- a) coding participant engagement as part of our fidelity checklist approach described in section 15.4 (both from session recordings and as part of our session observation checklist);
- b) self-report questionnaires assessing changes in each individual participants' weight management skills or behaviours (see Section 15.3);
- c) session attendance (the proportion of offered sessions that are attended);
- d) coding participant engagement in planned activities /intervention processes (such as goal-setting) as part of any session-observations;
- e) a 'progress tracker' in the self-help manual where planning and self-monitoring activities will be recorded by the participant this data may also be coded and summarised.

15.6 Supervision and Feedback sessions

A semi-structured supervision session for the intervention facilitators will be provided twice during each delivery period (see Gantt chart in Appendix 1). This will be an opportunity to share ideas/good practice, problem-solve, and provide and discuss formative feedback based on the above reviewing of recorded sessions. The supervision sessions will be conducted by teleconference to pool learning across intervention providers, and these sessions will also be recorded.

15.7 Satisfaction questionnaires

Questionnaires for participants to assess feasibility, satisfaction and ideas for improvement will be given a) after each participant-provider contact and b) at 6 months (end of intervention). We will give a similar questionnaire to the intervention facilitators as part of the 'contact sheet' described below. The questionnaires will contain mainly open-ended questions and a single satisfaction/overall feasibility question with a Likert response scale.

15.8 Facilitator contact sheet

A facilitator contact sheet will be completed following each participant interaction. This will record attendance, contact type (e.g. face-to-face, telephone) and duration and will also ask the facilitator to make notes about what was covered, what went well in the session; what worked less well; what s/he could have done differently and what we could improve about the intervention materials or the delivery process. The importance of completing these sheets will be reinforced in the training and at supervision sessions.

SkiM study protocol v8 – 29.03.16

15.9 Facilitator interviews

Brief semi-structured interviews either by telephone or face-to-face will be conducted with all the intervention facilitators about their experiences of delivering the intervention at the end of each intervention period. Topic guides will be developed in consultation with the intervention development team and the co-applicants. A schedule of events for the Intervention Delivery and Process Evaluation is detailed in Appendix 3.

16 DATA ANALYSIS AND SAMPLE SIZE CONSIDERATIONS

16.1 Quantitative Analysis

[name] will lead the analysis of outcomes, under supervision from [name]. Recruitment, intervention concordance, measures-completion and attrition rates will be calculated using descriptive statistics with 95% confidence intervals. Accelerometer data analysis will use bespoke analysis algorithms to extract physical activity variables, and data will be processed with advice from [name] (School for Sports and Health Science, University of Exeter) using 'R' statistical software. The variance in continuous outcomes at each time point will also be reported using descriptive statistics. Given the feasibility nature of this study we do not propose to formally test for differences in outcomes and costs between study arms. However, we will report the mean and standard deviation or confidence intervals outcomes at baseline and for changes in scores between baseline and follow up time points.

Participant flow through the study will be summarised using the CONSORT diagram (adapted for complex non-pharmacological interventions)⁴⁵ and will include the number of recruitment letters sent, numbers consenting, numbers participating, number undertaking intervention, and number of completed outcomes. Any differences between the recruited sample and the wider eligible sample will also be reported descriptively.

16.2 Sample size considerations

The sample size is calculated to provide realistic estimates (and confidence intervals (CIs)) for the recruitment and study completion rates. The resulting sample size will also allow realistic estimates of the intervention concordance rate and provide an ample pool of participants for qualitative sampling. From recent UK-based trials of interventions to support dietary /physical activity change, it is estimated that 25-30% of those contacted will take part and 70-80% of these will complete measures at 24 months^{46, 47}With a 30% recruitment rate, in order to estimate the recruitment rate with 95% CIs of +/-8% at each site, we would need to approach 133 people at each site (and this would recruit around 40 people per site). If recruitment rates vary between 20 and 50%, the CIs on the estimated recruitment rate would still be acceptable (between +/-6.8 and +/-8.5%). The total sample size requirement for two sites is therefore 80.

This sample size will also allow realistic estimates of the intervention concordance and study completion rates (+/-9 or 10%, assuming 70-80% completion) and provide an ample pool of participants for qualitative sampling (to get feedback on the intervention) in both phases of

intervention development (we would have 2 groups of 10 people receiving the intervention in each phase at each site).

Each of our provider partners will supply 2-3 intervention facilitators (5-6 in total) to deliver the study interventions. It is considered that experience of providing 2-4 complete programmes for 10-20 participants each would give the facilitators sufficient exposure to the intervention to be able to comment on its feasibility and acceptability

If intervention concordance /attendance is lower than expected, we will recruit a higher number (up to 50% more) in the second round to ensure that: a) sufficient people get exposure to the intervention to allow us to get collect a meaningful amount of data on process issues such as acceptability and possible improvements to the programme; b) the facilitators get experience of running several groups; and c) the group size does not become too low to function effectively (if this does still occur, we will consider merging groups to keep the group size above 5 if possible).

16.2.1 Stopping conditions

We will consider not continuing on to a trial if a) any serious adverse events are reported or are revealed by the qualitative data that are attributable to the intervention or the study procedures and are deemed by the ethics committee and our independent clinical advisors to constitute an unacceptable risk for further research b) the recruitment rate is less than 15% of those approached c) loss to follow-up rates are greater than 15% per year (this would affect generalisability for a large trial) d) intervention attendance is less than 50% of offered contacts being taken up. These criteria will be developed further by the Project Management Group prior to analysis.

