6.2 Objectives

- 1. To assess the feasibility and acceptability of incorporating the SkiM intervention into existing community-based weight loss programmes.
- 2. To refine the SkiM intervention, including its content and delivery modes, and associated training materials, so as to optimise its individual tailoring, potential effectiveness and feasibility for incorporation into existing community-based weight management programmes.
- 3. To assess the feasibility and acceptability to study participants of recruitment, assessment and process evaluation strategies that may be used in a future trial of the SkiM intervention.
- 4. To determine rates of, and influences on, outcome measure completion, as well as intervention and study participant retention and attrition.
- 5. To estimate the resources needed for the planned future trial.
- 6. To select process and outcomes measures for use in a future trial.
- 7. To develop the framework for economic evaluation in a future trial.

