7 STUDY DESIGN

7.1 Summary of the study design

An action research approach ³⁵ will be used, in which the SkiM intervention is tested and developed in an iterative cycle, involving stakeholders (particularly the service users themselves) in all stages of the process. The cycle involves three iterations of the intervention: an initial version has been developed with the involvement of service users, providers and commissioners as well as academics in the field of health behaviour change; this will be subject to mixed methods evaluation including pre-post testing, the results of which will be used to develop a second iteration of the intervention, which will also be evaluated. A third version of the intervention will then be developed for formal testing in a randomised control trial. This iterative approach involving multiple stakeholders and a pre-post test design, will enable investigation of the feasibility of integrating the SkiM intervention into existing programmes, as well as issues of acceptability, demand and implementation ³⁶. It also facilitates the evaluation and further development of recruitment, assessment and retention methods to be used within a subsequent trial. It is expected that in a trial, the control group would receive best-practice

[figure not shown]
REC Ref: 15/SW/0126

SkiM study protocol v8 - 29.03.16

usual care, which would be an existing weight loss programme. Hence all participants would receive an active intervention, and the need for a control arm is less pressing in a feasibility study.

The intervention period is six months, with outcomes assessment at baseline, and at 6, 12 and 18 months post-baseline. Eighty participants will be allocated equally to one of two study arms with different programme formats: both will be group-based, but they will differ in the number of sessions and supplementary support available. The study will be staged into two cohorts of approximately 40 participants. These will be run sequentially and separated by a period of four months, during which process data collected from the first stage will be used to refine the intervention for delivery in the second phase. This design is illustrated in Figure 1.

Figure 1: Study design

STUDY PARTICIPANTS

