8 PARTICIPANT IDENTIFICATION

8.1 Method 1: Recruitment via the existing routes used by Intervention Providers

Recruitment to existing Tier 2 weight management services in Devon is through referral by a GP or other NHS health professional. In South Devon and Torbay, referrals are channelled to the Community Fitness Team (CFT) who provide a 12 week group-based weight management programme. In areas around Exeter, referrals are directed to Health Promotion Devon (HPD), a lifestyle hub that helps individuals select a programme from a number that have been commissioned, including group and one-to-one programmes. Trained staff from CFT or HPD staff speak with referred individuals by telephone for screening, information provision and direction to a weight management programme. During these calls, those people who have selected one of the programmes offered by our providers will be asked, using a standard script, if they would be interested in taking part in an extended version of the programme as part of a research study concerned with maintenance of weight loss. Those expressing an interest will be asked to consent to their contact details being given to the research team so that further information about the study can be supplied to them.

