11.2 Delivery of the intervention

Both providers have existing weight management programmes, delivered primarily through group-based contacts over a 3-month period. They include elements addressing dietary restriction and increased physical activity, but differ in their specific content, the practitioners leading them (e.g. health trainers and dieticians), and the types of supplementary support offered, for example as supervised gym sessions, walking groups or cookery classes.

The augmented programmes will be adapted so that they are spread over a 6-month period, with up to 4 additional meetings in the programme schedules to ensure sufficient opportunity to address weight loss maintenance issues.

Both programmes will be supplemented by additional Skim-specific forms of support

- 1. A self-help manual, written by the research team and addressing the key elements of the Skim intervention
- 2. An automated telephone text service, in which personalised texts will be sent regularly to each participants, reminding them to self-monitor by measurement of their weight. The service will enable the individual to reply with their most recent weight measurement and this data will be recorded automatically and made available to the practitioner leading their programme.

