14 STUDY MEASURES AND DATA COLLECTION

14.1 Trial feasibility measures

To assess the feasibility of a trial of the SkiM intervention, the following measures will be used:

- Recruitment rate (the proportions of participants sent an invitation letter who are enrolled)
- Study completion rate (the proportion of those starting the study who provide data at 18 months). Reasons for dropout or loss to follow-up will be recorded where possible.
- Outcomes completion rates (proportions of participants who complete each measure at each time point)
- Intervention attendance (the proportion attending ≥ 66% of maintenance intervention sessions).

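### The recruitment rate used to judge a future randomised trial is observed under a guaranteed offer of the extended programme, so a rate of 15% or more does not by itself show that a randomised trial can recruit.

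*Protocol*

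**What the plan says.** Section 14.1 of the Protocol lists, as the first measure of the feasibility of a trial, "Recruitment rate (the proportions of participants sent an invitation letter who are enrolled". Section 8.3 collects recruitment counts by route to inform recruitment to a full trial. Section 16.2.1(b) then names as a ground for considering not continuing that "the recruitment rate is less than 15% of those approached". It adds that "These criteria will be developed further by the Project Management Group prior to analysis".

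The offer made in this study is fixed. Under section 8.1, people who have been referred and have already chosen a provider's programme are asked "if they would be interested in taking part in an extended version of the programme as part of a research study". Section 11.2 gives every enrollee the longer programme: "The augmented programmes will be adapted so that they are spread over a 6-month period, with up to 4 additional meetings", with a self-help manual and a text service as well. Sections 9.1 and 9.2 send referral-route decliners back to their standard programme. Decliners from GP lists are told that referral to a standard programme is possible.

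Section 7.1 expects trial controls to receive an existing weight loss programme, and section 17 describes the trial comparison as SkiM added to usual care against usual care alone. Section 7.1 reasons that, since all trial participants would receive an active intervention, "the need for a control arm is less pressing in a feasibility study".

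**The concern.** The rate measured here and the rate it is meant to inform answer different questions. Here a person says yes to a longer programme that is certain to be provided. In the trial, the same person would have to accept a chance of receiving only the existing programme. For someone on the referral route, that control arm is roughly what declining already gives, with study assessments added.

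The argument in section 7.1 is that all trial participants would be actively treated. That may bear on outcomes and retention. It does not address whether people would agree to have the programme decided by chance.

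At stake is Objective 3, "To assess the feasibility and acceptability to study participants of recruitment, assessment and process evaluation strategies that may be used in a future trial". If uptake here is comfortably above 15%, the trial team may plan recruitment on a figure that randomisation would lower, and nothing collected in the study would tell them by how much.

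**Working it through.** **1. The plan's own figures.** Section 16.2 expects 25-30% of those contacted to take part, approaches 133 people per site, and states a 95% CI half-width of 8 points at 30%, and of 6.8 to 8.5 points for rates of 20% to 50%.
- Number approached: 40/0.30 = 133.3.
- Half-width 1.96 × √(p(1−p)/133): 7.8 points at p = 0.30, 6.8 at 0.20 and 8.5 at 0.50.

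These agree with the Protocol. The precision calculation is sound, so the question is what the rate represents.

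**2. Direction.** A person who agrees to be randomised must be willing to accept either arm. A person enrolling here need accept only the SkiM arm. With the same routes, people and study burden, trial uptake therefore cannot exceed uptake of the guaranteed offer.

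**3. Size, under an assumption.** Let r be the observed rate and w the share of enrollees who would also have accepted randomisation. The documents give no value for w. Trial uptake is r × w, and it falls below 15% when w < 0.15/r:

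| Observed rate r | Break-even w |
|---|---|
| 20% | 0.15/0.20 = 75% |
| 25% | 0.15/0.25 = 60% |
| 30% | 0.15/0.30 = 50% |

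Read the other way, the observed rate needed for 15% in a trial is 0.15/w: 16.7% at w = 0.9, 20% at 0.75, 25% at 0.6 and 30% at 0.5.

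**4. Would the trigger notice?** Take 2 × 133 = 266 approached, true uptake of the guaranteed offer of 20%, and w = 0.6 as an assumed value. Trial uptake would be 0.20 × 0.6 = 12%. The observed rate reaches 15% (at least 40 of 266) with binomial probability 0.98, so the trigger would almost never fire.

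**5. Does anything planned measure w?** No.
- The Study Process Questionnaire (14.3) covers assessment burden, at 6 months, in participants only.
- Reasons for declining (9.1, 9.2, 10.1) are voluntary and concern the guaranteed offer.
- The schedules in Appendices 2 and 3 contain no item on accepting randomisation.

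**6. How well could w be estimated?** With 40 to 60 enrollees in the second cohort and w near 60%, the half-width is 1.96 × √(0.6 × 0.4/40) = 15 points, or 1.96 × √(0.6 × 0.4/60) = 12 points. If enrollees split equally between routes, each route has 20 to 30 people and half-widths of about 21 to 18 points.

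**The case against.** The strongest reply is that the criterion is one-sided. Section 16.2.1 says the team will consider not continuing below 15%; it does not say that 15% or more means proceed. A reader might infer a go rule, but the document does not state one, and the criteria are still to be developed by the Project Management Group. If the observed rate tends to be too high, a result below 15% even under the more attractive offer is a sound warning. This stands, and is why the trigger itself need not move. Further development before analysis cannot, however, recover an answer that was never asked for.

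Second, the planned 25-30% is drawn from two cited studies whose titles in the reference list describe randomised trials. Discounting that benchmark by w may count randomisation twice. This stands too: the break-evens apply to whatever rate is observed here and do not correct the planning figure.

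Third, a reader might infer that the observed rate is a strict upper bound. It is one only other things equal. This study asks for recording of all intervention contacts as part of consent (15.2), questionnaires after every contact (15.7) and recruitment within two months per cohort (10.6). A trial might relax these.

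Fourth, the argument that controls gain only assessments fits the referral route, expected to supply 20 of 40 people per cohort (10.6). People from GP lists have not already chosen a programme, so a control arm would itself offer them one, and the wording of their leaflet is not shown. The overstatement is likely to be smaller there.

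Last, having no control arm is an openly reasoned choice, and testing randomisation is not among the objectives. That is accepted; the point concerns how the recruitment rate is read.

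**Conclusion.** The mismatch is in the text: sections 8.3, 14.1 and 16.2.1(b) use the rate to judge a future trial, but it is uptake of a guaranteed extended programme, and willingness to be randomised is not recorded. The rate is likely to overstate trial uptake, other things equal and mainly on the referral route.

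The size is unknown. At an observed 25-30%, 40-50% of enrollees would have to refuse randomisation before trial uptake reached 15%, so there is real room; at 20% there is much less. A reader might conclude that a trial would fail to recruit, or that the 15% should be re-based on an adjusted rate. The documents support neither: they give no w, and a hypothetical answer from 40 to 60 people is too imprecise to carry a decision threshold. What holds is narrower. A rate below 15% is a valid stop signal, and a rate of 15% or more does not by itself show that a randomised trial can recruit. This is worth correcting as a cheap improvement and does not undermine the study.

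**What to change.** - **Sections 9.1/9.2:** for second-cohort recruitment, add one scripted question to the telephone call: would the person take part if allocation to the existing or the extended programme were by chance?
- **Section 14.1:** report the share answering yes among enrollees, by recruitment route, with a 95% CI. Report decliners' answers separately and do not pool them, because the multiplier in r × w refers to enrollees only.
- **Section 16.2.1(b):** keep the 15% trigger on the observed rate. State that a rate below 15% is a valid stop signal, and that a rate of 15% or more, observed without randomisation, does not by itself show that a randomised trial can recruit. Show the observed rate multiplied by the enrollee share beside it as a sensitivity figure.

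The cost is one question on a call already planned and a few sentences of text. This version is dated 29.03.16; first-cohort recruitment was scheduled for August to October 2015 and second-cohort recruitment for July to September 2016, so only the second cohort can be asked. The answer is hypothetical, its interval is wide overall and wider by route, and the figure carried forward may look less favourable.
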